### **Recruitment and Pre-Assessment**

All participants are recruited following the same enrollment protocol: Initial contact, screening, and pre-assessment. For *the initial contact*, the research coordinator will receive names of potential participants from the Clinical Trials Unit at Baycrest. The files of these individuals will be acquired from Sam & Ida Ross's Memory Clinic. Their contact information and diagnosis will be noted. They will then be contacted using a prepared telephone script. Those individuals who show interest in the study will then be scheduled a screening with [name] [name].

This *screening* can be done in person at Baycrest, or virtually over Zoom, and the participants can choose a particular modality if they have a preference. During the screening, [name] will go over the consent form with the participant, including the mechanics, history, and side-effects of tDCS, and the planned study design (i.e., what participation would entail schedule-wise). The screening also allows [name] to evaluate subjectively if the person may be too impaired for the study (for example, if they are unable to communicate or answer questions during the screening). If this scenario were to arise, [name] would explain to the participant, and

presumed caregiver, that the person is too impaired for the study. The screening is also an opportunity for the potential participant to ask any questions they might have. Assuming the participant is agreeable to participating in the study, a pre-assessment will be scheduled.

[figure not shown]
In this *pre-assessment*, the participant will be asked to complete versions of the tasks that will be administered during the study. In this manner, we can further verify that the potential participant is a good candidate for completing the study. Assuming they are able to successfully complete the tasks during the pre-assessment, and continued to be interested in participation, he or she would then be formally enrolled and scheduled into the study. Otherwise, the participant would be explained that they are unable to be enrolled into the study because they are unable to successfully complete the tasks planned. Because tDCS is an interactive therapy (a targeted behaviour must occur while the stimulation is administered), it is crucial that participants be able to complete the planned tasks, and simply receiving tDCS passively (i.e., while doing nothing) would be largely, if not completely, ineffective.

### **tDCS Parameters**

As done in our previous three-round study where naming training was paired with tDCS [5], stimulation will last for 20 minutes, concurrent with the beginning of the session. The anode electrode placed will again be placed over the IPL and the cathode over the right supraorbital region. Figure 2 shows the expected stimulation pattern.

[figure not shown]

Figure 2: Expected Stimulation Pattern from tDCS Montage

### Initial Assessment

In the first week, all participants will receive an initial assessment to gather demographic information (age, sex, years of education, racial background, and hand preference) and conduct a formal evaluation of participants. Evaluation includes the Montreal Cognitive Assessment (MoCA; [26]) and the Mini-Mental State Exam (MMSE; [27]) to assess the level of cognitive function. The Naming Task of the Cambridge Semantic Battery will be given to verify the presence of anomia (an inclusion criterion of the study). From these tasks, participants' impairment scores will be calculated. *Cognitive severity* will be measured as the combined total from the MoCA and MMSE ( $x/30 + x/30$ ). In contrast, *baseline severity* will be measured as the score obtained on this naming task. Assuming inclusion criteria are met, participants in the first week will also complete a structural MRI [view MRI protocol – page 11]. We will use SPM 12 to calculate a person's skull thickness and grey matter volumes around the IPL, as well as the CSF level, which will be quantified relative to the overall skull size of the participant.

## **Baseline Evaluation**

Neither the evaluators nor the participants will be told if the tDCS they received during the training sessions was 2mA, 4mA, or SHAM. Therefore, the study will be double-blind. The first session of each round will consist of a baseline evaluation prior to the training session where participants will be asked to name presented images from two lists: one that will be subsequently trained that round, and a second list that will be left untrained. By administering two lists during evaluation, one trained, one untrained, we can examine the impact of tDCS on training, and if this improvement generalizes to an untrained naming list. General Cognitive Status, as measured by the MoCA and MMSE. Mood, assessed by the Geriatric Depression Scale (GDS, [35]).

## **Training Sessions**

The language training protocol will be the same we have previously published [5], which successfully improved naming in people with dementia. All training sessions will have the same format and involve the administration of tDCS combined with training. More specifically, during the first 20 minutes, a research participant will give sham or tDCS set at 2mA or 4mA for 20 minutes. After a research assistant has set up the tDCS machine and started stimulation, the participant is presented 45 images (from Snodgrass and Vanderwart; [31]) individually on a laptop, one by one, and asked to name each item that appears. Items have a range of difficulty and familiarity, which ensures it can be used for participants with different levels of impairment; perfect scores and scores of zero are unexpected. The research assistant notes which items were incorrectly named. These misnamed images will then be ranked in familiarity from the most familiar to the least familiar, based on norms collected in our lab. The five most familiar missed items will form a five-item study group. The trainer then presents each item of the study group one by one to the participant, naming each item in front of the participant. Next, the five images are presented one by one again,

but now the participant is asked to name them. When participants have difficulty remembering the name of the item, the trainer will give phonological cues (starts with a . . .) or semantic cues (In Halloween, you carve a . . .). This group of items is then shown again one by one a second and a third time, each time noting if the participant can correctly name it.

After the study group is presented three times, those items correctly named by the participant three times in a row without cues are replaced with the next most familiar item that was missed at the beginning of the session. Thus, when the study group is presented a fourth time, it contains images that the participant still hasn't named three times in a row or new items that replaced ones named three times in a row. The training session will continue in this manner, replacing items named three times in a row, maintaining those yet to be named successfully three times, until all items missed at the beginning of the session are incorporated into the study group and trained with the participant.

In summary, training sessions have participants practice picture naming, as might occur in a typical speech therapy session for anomia, except the first 20 minutes are concurrent with tDCS, which is typical in tDCS studies. Most sessions will last around an hour. Due to the training involved, we expect participants will improve regardless of the stimulation condition but predict this improvement will be larger when done with real tDCS, and largest when done with 4mA tDCS. Related to this, we will check if this superiority of 4 mA over 2 mA is related to a participant's condition (e.g., sex, level of atrophy).

### **Subsequent Evaluations**

For each round, in addition to the evaluation just before the first stimulation session, an additional evaluation will take place during the final training session, and two weeks later after the

final session. In this manner, we can obtain a baseline measurement, check for post-stimulation changes, and if those changes have continued two-week's post-stimulation.

### **Structural MRI Protocol**

Participants will undergo a Structural MRI at Baycrest. The protocol has been informed to the MR Technicians (please see attached documents). The Project Coordinator will book the MR suite using the Baycrest MR Web Scheduler with a 72 hour notice at the least.

Participants will be asked to arrive 15 minutes before their scheduled scan to review and fill the consent and MR screening forms. The participant will then be escorted to the Interview room to be interviewed by a Level 11 MR Personnel with respect to their MR screening form and medical history prior to changing for the MR exam. After changing, the MR technologist will escort the research participant into the magnet room and the accompanying researcher (Assistant, Coordinator or PI) to the control area. Post scanning, the lab member accompanying the research participant will monitor the change process, and other processes outlined in the "MR Research Suite Process Baycrest – RRI."

To be able to successfully perform the MRI, lab members will undergo the Virtual MR Safety Training & Orientation session and will also receive an in person suite tour.

### **Planned Analyses**

The primary outcome measure will be improvement on the naming lists administered, both a trained version and an untrained version. Improvement will be measured in terms of the number

of images correctly named post-training compared to baseline. A repeated-measures ANOVA will be run to compare the three stimulation conditions (SHAM, 2mA, 4mA) with sex (male, female) as a between-subject variable. This analysis will be conducted separately for the trained and untrained items. We expect to find the greatest improvement in the 4mA condition.

Next, we will calculate how much a participant improved in each condition by taking the naming score obtained at baseline for a naming list and subtracting it from the naming score obtained in the final stimulation session (e.g., 32 (final) – 20 (baseline) = an improvement score of 12). These scores are then used to produce tDCS effectiveness scores: the improvement score in the 4mA condition minus the improvement score in the SHAM condition; and the improvement score in the 2mA condition minus the improvement score in the SHAM condition. These tDCS effectiveness scores will then be the dependent variables in a multivariate logistic regression; once for trained items, one for untrained items. The predictors will be the CSF level of a participant, grey matter volumes and skull thickness around the IPL, impairment scores (baseline and cognitive severity), and interactive terms representing the sex of the participant. In this manner, we can examine what individual differences predict the tDCS response in people with AD, and if these predictors are the same for 2mA and 4mA tDCS, while checking for sex differences. We expect more significant levels of CSF, less IPL grey matter, thicker skulls, and greater impairment levels will be predictive of more substantial improvement in the 4mA condition because this stimulation intensity is needed to compensate for higher levels of shunting and severity. CSF and grey matter values may be less predictive for how well women respond to tDCS as their relatively smaller heads could compensate for increased shunting levels.

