## METHODS:

### Sample

Based on the previous study where tDCS was used for language training [6], we expect a partial eta square around 0.20. For 80% power to detect a difference across the three levels of intensity, while also accounting for the sex of a participant, a repeated-measures ANOVA test at an alpha level of 5% will require 54 participants with AD (27 men and 27 women). To compensate for anticipated attrition over the study, we will recruit a sample of 30 men and 30 women, 60 total.

These participants would have received the diagnosis of probable AD from Baycrest's Memory Clinic expert staff [29, 30] according to standard clinical criteria. Only patients with no family history of epilepsy and who can give consent will be tested. We will seek people with mild to

moderate AD (Reisberg stages 3, 4, or 5, [34]) who score between 18 and 25 on the MoCA [26]. Participants must show no history of stroke or traumatic brain injury, nor shunts or metal in the head that could interfere with the delivery of tDCS. Finally, people will have no evidence of significant heart disease, alcoholism, drug use. All enrolled participants will be expected to complete an MRI; however, if they are unable to complete an MRI due to the presence of an exclusion criterion, they will still be allowed to complete all subsequent stages of the study. Participants will be evaluated and trained using different naming lists each round. We have developed equivalent versions of these naming lists in our lab, which allows us to use a different trained and untrained list each round.

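### Two naming lists are both primary and tested separately, with no rule for combining them; if either list may carry the claim, the false-positive risk is up to 9.75%

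*Protocol*

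**What the plan says.** The Planned Analyses section of the protocol defines the primary outcome over two lists: "The primary outcome measure will be improvement on the naming lists administered, both a trained version and an untrained version". It then specifies a repeated-measures ANOVA across SHAM, 2 mA and 4 mA, "with sex (male, female) as a between-subject variable", and adds: "This analysis will be conducted separately for the trained and untrained items". So there are two primary tests.

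The Sample section works with one test. The target is "For 80% power to detect a difference across the three levels of intensity, while also accounting for the sex of a participant", and the result is that "a repeated-measures ANOVA test at an alpha level of 5% will require 54 participants with AD". The effect size is given once, without saying which list it belongs to: "we expect a partial eta square around 0.20".

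The main hypothesis under Hypotheses Addressed predicts greater improvement at 4 mA and mentions neither list. No section ranks the lists, divides alpha, sets an order of testing or says what happens if the lists disagree.

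**The concern.** How two primary results combine is part of defining the primary outcome. The protocol fixes two tests for one hypothesis and leaves open which pattern of results confirms it. A significant effect on one list only could be reported as confirmation, as partial confirmation or as failure, and nothing in the document prevents that choice from being made once the results are known.

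What is at stake is the error rate behind the trial's main claim. Two unadjusted tests at 5% do not hold 5% for the statement that at least one list showed a difference between intensities. They do hold it for the statement that both did.

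**Working it through.** **Inputs from the protocol.** Two primary ANOVAs (Planned Analyses). Alpha 0.05, power 80%, partial eta squared 0.20, 54 evaluable participants as 27 men and 27 women (Sample). Three within-subject conditions and two sex groups give an F test of the condition effect on 2 and 2 × (54 − 2) = 104 degrees of freedom under sphericity.

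**Assumptions, because the protocol gives no figure.** The correlation between the two lists is varied from 0 to 0.95. Each ANOVA is tested at 0.05.

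**1. The plan's own figure.** Partial eta squared 0.20 gives f² = 0.20/0.80 = 0.25. The N for 80% power at alpha 0.05 depends on how the noncentrality λ is formed:

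| Convention for λ | N for 80% power | Power at N = 54 |
|---|---|---|
| f² × 3N/(1 − 0.5), assuming correlation 0.5 between conditions | 9 | above 99.9% |
| f² × error df = 0.25 × 104 = 26 at N = 54 | 23 | 99.7% |
| f² × N = 0.25 × 54 = 13.5 at N = 54 | 41 | 91.1% |

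None returns 54. This does not affect the error rate below, but it makes the power cost of a correction depend on which stated input is trusted.

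**2. False positives if either list suffices.** With independent lists:

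1 − (1 − 0.05)² = 1 − 0.9025 = 0.0975.

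The Bonferroni bound is 0.05 + 0.05 = 0.10. The two ANOVAs were simulated under the null with N = 54 and 100,000 runs per correlation. Each alone rejected in 4.9% to 5.1% of runs. At least one rejected in:

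| Correlation between lists | At least one false positive |
|---|---|
| 0 | 9.7% |
| 0.3 | 9.5% |
| 0.5 | 9.2% |
| 0.7 | 8.5% |
| 0.8 | 7.9% |
| 0.9 | 7.1% |
| 0.95 | 6.6% |

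**3. False positives if both lists are required.** The joint event cannot be more likely than either single rejection, so the rate is at most 5%.

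**4. Power per list at N = 54 if alpha is fixed at 0.025.**

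| Reading of the Sample section | Alpha 0.05 | Alpha 0.025 | Loss (points) |
|---|---|---|---|
| λ = 26 | 99.7% | 99.2% | 0.5 |
| λ = 13.5 | 91.1% | 85.4% | 5.7 |
| Stated 80% at N = 54 taken at face value (λ about 9.9) | 80% | 71% | 9 |

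**5. Power per list with Holm.** A list is declared significant if p ≤ 0.025, or if p ≤ 0.05 and the other list has p ≤ 0.025. With the same effect on both lists and independent test results, power is P(0.025) + [P(0.05) − P(0.025)] × P(0.025):

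- λ = 13.5: 0.854 + (0.911 − 0.854) × 0.854 = 0.903, a loss of about 1 point.
- 80% at face value: 0.71 + (0.80 − 0.71) × 0.71 = 0.774, a loss of about 3 points.

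**The case against.** The strongest objection is that a multiplicity rule is the kind of detail a protocol leaves to the statistical analysis plan, which is not shown and may contain one. That stands as far as the choice of adjustment method goes. It does not dispose of the point, because the protocol itself names two primaries, fixes two tests and sizes the trial on one; what counts as a positive primary result is left undefined where it is set up.

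A second objection is that the lists ask different questions. The Baseline Evaluation section uses the trained list for the effect on training and the untrained list for generalisation. If each list supported only its own claim, the need for adjustment would be a matter of judgement. But the hypothesis is not divided that way, and both lists are called primary.

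A reader might infer more than the documents support:

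- **That the trial's error rate simply is 9% to 10%.** That needs an either-list rule, which the protocol does not state, and lists that are at most moderately correlated. Both lists are named by the same participants in the same rounds, so correlation is plausible, but no value is given.
- **That a stated 5% overall error rate is broken.** The 5% is an input to the sample-size calculation for one ANOVA. No trial-wide rate is claimed, and each ANOVA alone holds 5%.
- **That correction is free.** The loss is below 1 point only at λ = 26.
- **That the team's earlier study shows a one-list result is likely.** In the Preliminary Studies section, intensity mattered for untrained but not trained items. However, that study measured N-back response times in a mixed dementia group with frontal stimulation. It shows that lists can diverge, not that they will here.

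**Conclusion.** The point holds in conditional form. The protocol sets two primary outcomes with separate tests and does not say how they combine. If significance on either list is taken to confirm the 4 mA hypothesis, the chance of at least one false positive is up to 9.75%, and about 7% to 9.75% for correlations of 0.9 down to 0. If both lists are required, it is at most 5%.

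The figures assume each ANOVA is run at 0.05, sphericity, N = 54 and no adjustment rule elsewhere. The between-list correlation is assumed, so the range should be quoted rather than a single value. The gap should be closed, since the protocol permits readings on both sides of 5%.

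**What to change.** Before unblinding, add one sentence to Planned Analyses taking one of two routes:

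- apply Holm to the trained-list and untrained-list ANOVAs at an overall 5%; or
- name one list as primary at 5% and test the other, also at 5%, only if the first is significant.

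Either holds the overall error at 5% or below whatever the correlation. Requiring both lists would also control it, but lowers the chance of success: with 80% power on each and independent results, 0.80 × 0.80 = 64%.

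No extra participants are needed to control the error. The price is power per list. The worst case is a fixed alpha of 0.025, which costs under 1 to about 9 points; Holm costs less when both lists show an effect. On the stated effect size, power at N = 54 stays at 85% or more even at 0.025. If the stated 80% is taken literally instead, per-list power would fall to about 71% at 0.025, or about 77% with Holm under the assumptions in step 5. The ordered route costs the first list nothing, but the second cannot be claimed if the first fails. The sponsor should therefore choose the order on scientific grounds.

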## **Hypotheses Addressed**

The degree of improvement observed in people with Alzheimer's disease will be significantly greater when training is carried out at higher stimulation intensity (4mA vs. 2mA, SHAM).

There will be significantly more significant improvement observed when:

[figure not shown]
1. Individuals have more atrophy (decreased brain volume, higher CSF volume).
2. Individuals have a higher degree of impairment
3. The participant is female (possibly due to skull differences).

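### The named primary test and the stated 80% power address any difference among SHAM, 2 mA and 4 mA, not the hypothesised advantage of 4 mA over 2 mA

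*Protocol*

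**What the plan says.** - **Hypothesis (Protocol, Hypotheses Addressed).** The degree of improvement will be "significantly greater when training is carried out at higher stimulation intensity (4mA vs. 2mA, SHAM"). This is directional and pairwise: 4 mA against 2 mA, and 4 mA against SHAM.
- **Primary test (Protocol, Planned Analyses).** "A repeated-measures ANOVA will be run to compare the three stimulation conditions (SHAM, 2mA, 4mA) with sex (male, female) as a between-subject variable". It is run separately for trained and untrained items, and both lists are named as primary. The next statement is an expectation with no test attached: "We expect to find the greatest improvement in the 4mA condition".
- **Sizing (Protocol, Sample).** "For 80% power to detect a difference across the three levels of intensity", allowing for sex, at alpha 5% and an expected partial eta squared of about 0.20, the protocol gives 54 participants (27 men, 27 women) and recruits 60.
- **Difference scores (Protocol, Planned Analyses).** Two are defined. One is "the improvement score in the 4mA condition minus the improvement score in the SHAM condition". Its counterpart is formed in the same way for 2 mA against SHAM. Both are outcomes for the regression on individual predictors, not tests of the mean intensity effect.

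The protocol names no 4 mA versus 2 mA comparison of mean improvement.

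**The concern.** The F test of a three-level factor asks whether the three means are all equal. It rejects for any departure from equality, including the case where 2 mA and 4 mA work equally well and both beat SHAM. In that case the statement that raising the intensity helps is false, yet the named primary test is likely to be significant.

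That case cannot be dismissed here. The protocol describes 2 mA as the conventional intensity and reports that the group has already seen naming improve with tDCS. The new question is therefore 4 mA against 2 mA. The section on communication of results also anticipates presenting data on 4 mA relative to both SHAM and 2 mA. A significant F with the highest observed mean at 4 mA would not be enough for that claim, and the 80% power does not carry over to it.

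**Working it through.** **Inputs from the protocol:** partial eta squared 0.20, alpha 0.05, N = 54, two sex groups, three within-participant conditions. **Assumptions:** sphericity, and the share s of the 4 mA benefit that 2 mA delivers, which the protocol does not give.

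**Step 1. The plan's own figure.** f² = 0.20/(1 − 0.20) = 0.25. Error df = (54 − 2) × (3 − 1) = 104. The 54 is not reproduced from these inputs: for the condition effect, the conventions tried need 10 to 42 participants for 80% power. The point does not depend on this, so three readings of the noncentrality λ are carried through:

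| Reading | λ | Power of F (2, 104 df) |
|---|---|---|
| Stated 80% at N = 54 taken at face value | 9.92 | 0.80 |
| λ = f² × N = 0.25 × 54 | 13.5 | 0.911 |
| λ = f² × error df = 0.25 × 104 | 26 | 0.997 |

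The face-value reading corresponds to a partial eta squared of 0.155 (9.92/54 = 0.184; 0.184/1.184) or 0.087 (9.92/104 = 0.095; 0.095/1.095), not 0.20. It is the pessimistic end.

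**Step 2. The F when 4 mA equals 2 mA.** Power of the F depends on λ alone, not on which means differ. The right-hand column therefore also applies when SHAM, 2 mA and 4 mA have means 0, 1, 1: the F rejects with probability 0.80, 0.911 or 0.997. A simulation of this pattern at partial eta squared 0.20 (20,000 runs) gave 0.9975 for the F and 0.0496 for the 4 mA–2 mA comparison, which is only its type I error.

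**Step 3. Power of the 4 mA–2 mA contrast.** Let the means be 0, s, 1. The contrast carries a fraction [(1 − s)²/2] / SS of the condition effect, where SS is the sum of squared deviations of the three means from their average. At s = 0.5, SS = 0.25 + 0 + 0.25 = 0.5 and the fraction is 0.125/0.5 = 25%. The contrast noncentrality is λ times this fraction, on 1 and 104 df:

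| 2 mA share s (assumed) | Fraction | λ = 9.92 | λ = 13.5 | λ = 26 |
|---|---|---|---|---|
| 0 | 75% | 0.771 | 0.883 | 0.992 |
| 0.25 | 51.9% | 0.613 | 0.746 | 0.954 |
| 0.50 | 25% | 0.345 | 0.444 | 0.714 |
| 0.75 | 5.8% | 0.116 | 0.141 | 0.228 |

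Contrast power stays at or above 80% up to s = 0.18 (λ = 13.5) or s = 0.44 (λ = 26). At λ = 9.92 it does not reach 80% for any s from 0 upward.

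**Step 4. Contrasts after a significant F.** With three conditions, any two pairwise equalities together imply that all three means are equal. Testing each contrast at 5% only after a significant F at 5% is therefore a closed procedure within one list. In simulation with 4 mA = 2 mA > SHAM (40,000 trials per setting), the gated 4 mA–2 mA contrast was falsely significant in 4.7% to 5.0%. With all three conditions equal (20,000 trials), at least one of the two contrasts was claimed in 4.0%. The gate's cost in 4 mA–2 mA power at λ = 9.92 was 76.5% to 71.7% at s = 0, 60.6% to 58.0% at s = 0.25 and 34.3% to 33.4% at s = 0.5. At λ = 26 it was at most 0.1 point.

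**Step 5. Two lists.** The closure does not extend across trained and untrained items. If the lists were independent (an assumption), the 4.0% would become 1 − 0.96² = 7.8%.

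**The case against.** The strongest reply is that follow-up contrasts after an ANOVA are commonly left to the SAP, which is not shown. Moreover, the protocol never says that a significant F will be taken as proof that 4 mA beats 2 mA. Both statements are correct. The absence of a post-hoc procedure would not be a finding on its own, and no false decision rule can be attributed to the protocol. What remains is that the protocol itself states a pairwise hypothesis, one primary test and one sizing basis, and the last two do not isolate the first. A contrast added in the SAP would not change what the 80% was stated for.

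A reader might infer that the Sample section is wrong or that the trial is underpowered for 4 mA against 2 mA. The documents support neither. The 80% is correctly labelled as power for the overall difference, and contrast power runs from 12% to 99% over the assumed shares. The failure to reach 80% at any share comes only from the face-value reading, which does not correspond to the stated effect size.

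A reader might also infer that the predictor regression cannot show whether predictors differ between intensities, because both scores are taken against SHAM. That does not follow. The aim is to see "if these predictors are the same for 2mA and 4mA tDCS", and SHAM cancels when one score is subtracted from the other, so equality of coefficients can be tested in a joint model. The protocol nowhere says that predictors will be compared by which reach significance for each score.

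**Conclusion.** The mismatch stands and should be fixed before analysis. The primary F is a valid test that some condition differs, but it is insufficient for the intensity hypothesis: it rejects with probability 0.80 to 0.997 when 4 mA and 2 mA are equal and both exceed SHAM. The stated 80% does not transfer to the 4 mA–2 mA comparison, whose power at N = 54 is undetermined until a 2 mA share is assumed.

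The figures rest on sphericity, 54 evaluable participants, the three readings of the noncentrality, and shares that are assumptions rather than protocol values. The qualitative conclusion needs none of these: an F on three means does not identify which means differ.

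**What to change.** 1. **Planned Analyses.** Name the within-participant 4 mA–2 mA and 4 mA–SHAM contrasts as the test of the intensity hypothesis. One option is to test each at 5% after a significant overall F, which is closed for three conditions within one naming list. State plainly that, because the trained and untrained lists are both primary, this does not control error across the two lists.
2. **Sample.** Say that the 80% applies to the overall difference. Beside it, report 4 mA–2 mA power at the existing N over a stated range of 2 mA shares, with the noncentrality convention given.

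**Cost.** No new data or visits are needed, since each participant is measured under all three conditions. The cost is a rewritten analysis and power paragraph, a possibly less favourable stated power for 4 mA against 2 mA, and up to about 5 points of contrast power from gating (largest at a 2 mA share of 0 with the 80% taken at face value).
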